6.2 Endpoints

6.2.1 Primary Endpoints

The primary efficacy endpoint is the proportion of index subjects achieving Complete Cure at Day 28. Complete Cure is defined as demonstration of both:

- (1) Clinical cure (all signs and symptoms completely resolved, including burrows, inflammatory/noninflammatory lesions and pruritus).

and

- (2) Microscopic or dermatoscopic cure demonstrating the absence of mites, eggs, and/or scybala, and negative dermoscopy for burrows.

The primary safety endpoints are the incidence and severity of adverse events, changes in electrocardiograms (ECG), in laboratory parameters and changes in vital signs.

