9.4.5 Electrocardiograms

Twelve-lead ECGs will be performed before blood collection after the subject has been supine for approximately 10 minutes. ECGs will be performed in triplicate at Baseline (before randomization). After IP administration, another ECG will be performed at 3 hours (± 30 minutes) for the subjects in the PK subset. At Week 16, ECGs will be performed for all subjects. Repeat measurements will be performed if there are any abnormalities observed or artifacts are present. All ECG recordings will be reviewed by the Investigator or nominee and retained in the subject's study records.

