15.5.4 Safety Endpoints

- Incidence and severity of TEAEs.
- Incidence of serious TEAEs.
- Incidence of TEAEs leading to study withdrawal and/or death.
- Changes from Baseline in ECGs, laboratory assessments and vital signs.

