15.6.4.3 ECGs, Vital Signs and Physical Exams

The analysis of ECGs, vital signs and physical exams will be conducted similarly to laboratory assessment analyses.

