6.4 Safety Endpoints

- Incidence and severity of treatment emergent adverse events (TEAEs).
- Incidence of serious TEAEs.
- Incidence of TEAEs leading to study withdrawal and/or death.
- Incidence of TEAE attribution of relatedness to study drug.
- Changes from Baseline in 12-lead electrocardiograms (ECGs), laboratory assessments and vital signs.

Unless otherwise noted incidence refers to subject incidence.

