7 DEFINITIONS

Terminology	Definitions
Age	Age will be calculated based on the month and year of birth entered in the Demography eCRF page, relative to the month and year of informed consent.
Baseline	The last non-missing assessment immediately prior to exposure to study drug
BMI	Body Mass Index, calculated as $\text{Weight (kg)} / (\text{Height (m)})^2$ (kg/m ²).
Clinical Cure	Demonstration that all signs and symptoms have completely resolved, including burrows, inflammatory/noninflammatory lesions and pruritus.
Complete Cure	Demonstration of both: (1) Clinical cure (all signs and symptoms have completely resolved, including burrows, inflammatory/noninflammatory lesions and pruritus). and

CONFIDENTIAL

Terminology	Definitions
	(2) Microscopic or dermatoscopic cure demonstrating the absence of mites, eggs, and/or scybala, and negative dermoscopy for burrows.
Complete Cure without regard to pruritus	Similar definition as Complete Cure except the pruritus component is not included in the definition, e.g., (1) Clinical cure (all signs and symptoms have completely resolved, including burrows and inflammatory/noninflammatory lesions). and (2) Microscopic or dermatoscopic cure demonstrating the absence of mites, eggs, and/or scybala, and negative dermoscopy for burrows.
Concomitant Medication	Medication taken on the day of or after the first study drug exposure. Concomitant medication may start prior to study drug administration if continued on the day of/after study drug administration.
Dispensing Error	The subject was dispensed less than or more than 16 capsules of moxidectin and/or placebo, but received the assigned treatment
Dosing Error	The subject was dispensed 16 capsules of moxidectin and/or placebo, but did not receive the assigned treatment
Dosing and Dispensing Error	The subject was dispensed less than or more than 16 capsules of moxidectin and/or placebo, and also did not receive the assigned treatment
Investigator Assessed Cure	Investigator selection of one of the three categories below that best describes the cure status of the subject at Day 28: 1. The scabies infestation is clear with all signs resolved, 2. The scabies infestation is clear with incomplete resolution of signs, and no additional treatment with standard of care is warranted, 3. The scabies infestation is not clear and additional treatment with standard of care is warranted.

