9.12.3 Clinical Laboratory Assessments

All laboratory values (hematology and serum chemistry) will be converted to the International System of Units (SI) for the purposes of summary and listing.

Hematology and serum chemistry data will be listed separately including change from Baseline and flagging all out-of-range values. Toxicity grades will be derived where possible for each hematology and biochemistry result as described in Appendix 1 of the current protocol (The 2007 FDA Guidance for Industry: Toxicity Grading Scale for Healthy Adult and Adolescent volunteers Enrolled in Preventive Vaccine Clinical Trials). Those grades will be included in the listings.

Aggregate summary data for hematology and serum chemistry test results will be provided for Baseline and post-Baseline assessments. These analyses will include changes from Baseline, to be presented only for subjects with non-missing assessments at both timepoints. Means, medians, SDs, minimum, and maximum values will be provided for both test results and for the individual change from Baseline.

A summary tabulation will show the number and proportion of subjects for the serum and hematology laboratory abnormalities graded using the scales shown in Appendix 1 of the current protocol.

9.12.4 12-Lead ECGs

An overall summary table will be provided for normal and abnormal 12-lead ECGs in the SfAS and in the PK Analysis set for the Hour 3 ECG. Abnormal 12-lead ECGs will be summarized by treatment group and overall and by whether they were normal/abnormal and if abnormal, clinically significant or not significant. ECG data are collected at Baseline and Week 16 only for subjects not selected for the PK Analysis set.

All 12-lead ECG data will be listed.

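### Change from Baseline in ECG is a named safety endpoint, but the SAP specifies only normal/abnormal counts for it, and the Hour 3 table leaves out placebo

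*SAP*

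**What the plan says.** Protocol 6.2.1 states: "The primary safety endpoints are the incidence and severity of adverse events, changes in electrocardiograms (ECG), in laboratory parameters and changes in vital signs". Protocol 15.5.4 makes the reference point explicit, "Changes from Baseline in ECGs, laboratory assessments and vital signs", and SAP 6.4 repeats it: "Changes from Baseline in 12-lead electrocardiograms (ECGs), laboratory assessments and vital signs".

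On collection, Protocol 9.4.5 says "ECGs will be performed in triplicate at Baseline (before randomization"), and then "After IP administration, another ECG will be performed at 3 hours (± 30 minutes) for the subjects in the PK subset". All subjects have a further ECG at Week 16. The PK subset is about 20 subjects from each of the four arms (Protocol 9.4.8 and 10.1; SAP 5.1).

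On analysis, Protocol 15.6.4.3 says "The analysis of ECGs, vital signs and physical exams will be conducted similarly to laboratory assessment analyses". For laboratory data, Protocol 15.6.4.2 allows changes from Baseline and/or shift tables, but does not require them. SAP 9.12.4 gives the ECG analysis: "Abnormal 12-lead ECGs will be summarized by treatment group and overall and by whether they were normal/abnormal", with abnormal tracings further divided by clinical significance, and a full listing. It places the Hour 3 ECG in the PK Analysis Set. SAP 9.12.7 reissues the ECG tables at Week 16.

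SAP 7 defines Baseline as "The last non-missing assessment immediately prior to exposure to study drug". SAP 9.12 adds that when several measurements fall in one interval the last is used, or the worst if the last cannot be identified, and that all repeats are listed.

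**The concern.** SAP 6.4 names three measures together as change-from-Baseline endpoints. Vital signs and laboratory values each get a change analysis; ECG gets none. A subject with an unchanged Baseline abnormality and a subject who moves from normal to abnormal add equally to a post-dose count of abnormal tracings, and a resolution in one subject can cancel an onset in another.

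The gap is not declared. SAP 1.1 gives the SAP precedence over the protocol's statistical methods, and SAP 1.2, which lists the departures from the protocol, does not mention ECG. Under SAP 1.1, a change analysis added later would be labelled post hoc and exploratory.

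The second problem is at Hour 3, close to the median time of peak concentration (3 to 4 hours in Protocol 5.3.2.1). This is the only scheduled post-dose ECG available at the Day 42 analysis. The primary safety objective is comparison with placebo, yet the population named for this table is defined so that placebo subjects cannot enter it.

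**Working it through.** The documents give no ECG figure to reproduce, so the check sets endpoint against analysis and then works out what the specified table can show.

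**1. Endpoint against analysis.**

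| Measure | Change from Baseline named in SAP 6.4 | Analysis specified in the SAP |
|---|---|---|
| Vital signs | yes | values and change from Baseline by arm and time point (9.12.2) |
| Laboratory values | yes | values and change from Baseline in subjects with both assessments; graded abnormalities (9.12.3) |
| ECG | yes | normal/abnormal counts, abnormal split by clinical significance; listing (9.12.4); tables reissued at Week 16 (9.12.7) |

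The SAP names no ECG interval, no change score, no shift table and no ECG-specific rule for the triplicate.

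**2. What counts can show.** In one arm with complete data, let a be the number abnormal at Baseline, r the number who resolve and e the number newly abnormal. The post-dose count is a - r + e. Even if Baseline is tabulated beside it, the difference is e - r. The safety question concerns e, which the counts do not identify. If some subjects lack the later ECG, e - r is not identified either.

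**3. Illustrative size.** Assume 10-20% abnormal at Baseline, with n = 50 per arm.
- Carried forward per arm: 0.10 x 50 = 5, to 0.20 x 50 = 10.
- SD of the chance difference in Baseline counts between two arms, sqrt(2 x n x p x (1 - p)): sqrt(2 x 50 x 0.10 x 0.90) = 3.0; sqrt(2 x 50 x 0.20 x 0.80) = 4.0.
- Two new abnormalities in one arm: 2/3.0 = 0.67 SD, or 2/4.0 = 0.50 SD.

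With no resolutions, the post-dose count would be 7-12 in that arm against 5-10 in an arm with no new cases. A shift table would show 2 against 0. That contrast is clearer but not decisive: the two-sided Fisher p is 2 x (50 x 49)/(100 x 99) = 0.495.

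**4. Hour 3 population.** SAP 8.6 requires at least one dose of moxidectin and at least one quantifiable concentration. Placebo subjects meet neither condition. Yet Protocol 9.4.5 takes the Hour 3 ECG in the whole PK subset, and Protocol 9.4.8 and SAP 5.1 draw that subset from all arms to protect the blind. About 20 placebo subjects therefore have the ECG and are not in the table. SAP 6.3 describes the sampled subset as the moxidectin cohorts only, which conflicts with SAP 5.1 and should be reconciled.

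**5. Baseline category from three readings.** Suppose each independent reading has a 10% chance of being called abnormal at random.
- Last reading: 10%, the same as a single post-dose reading.
- Majority (median category) of three: 3 x 0.1^2 x 0.9 + 0.1^3 = 2.8%.
- Worst of three: 1 - 0.9^3 = 27%.

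Worst of three makes Baseline look more abnormal than one post-dose reading would, and so hides new abnormalities.

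**6. Intervals, if they are in the database.** With within-subject variance s^2, independent replicates and one post-dose reading, the variance of change is 2s^2 from a single Baseline reading and s^2(1 + 1/3) = 1.33s^2 from the mean of three, a reduction of one third. Variation shared by replicates taken on the same occasion makes the gain smaller, so one third is a ceiling.

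**The case against.** The case for leaving the plan alone has five parts.

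- **The protocol wording is permissive.** Change or shift tables are optional there, so the SAP breaks no firm commitment on method. This stands. It does not remove the endpoint, which both documents define as a change from Baseline.
- **The clinical-significance split and exclusion criterion 7 limit carry-over.** ECG findings judged a risk or a confounder exclude a subject, so most persistent abnormalities should fall in the not-significant row. This stands, and it makes the counts more readable than a bare normal/abnormal table. It does not separate new findings from old within that row.
- **Other outputs cover part of the question.** Under Protocol 12.2 and 12.5.1, a new or worsened ECG finding judged an adverse event and not explained by a diagnosis is recorded as one, and is then tabulated by arm as a TEAE. The listing lets a reader trace each subject. Neither is a by-arm summary of ECG change for findings not called adverse events.
- **Table layout is left to separate specifications.** These were not seen and might contain a shift table. The finding is therefore limited to what the SAP specifies.
- **SAP 9.12.4 may mean the PK subset.** It speaks of subjects not selected for the PK Analysis Set, which suggests the sampling subset was intended. That may be so, but SAP 8.6 defines the named set and excludes placebo.

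Three stronger readings are tempting and unsupported. ECG change is not the sole primary safety endpoint; it stands beside adverse events, laboratory values and vital signs. The protocol gives no purpose for the triplicate, and the Baseline ECG also serves eligibility review before randomization (Protocol 9.3.2), so it cannot be said to have been collected for a change analysis. Nor can it be said that two replicates are discarded or that no ECG change will ever be produced: all readings are listed, and the table specifications are unknown.

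**Conclusion.** The mismatch is real. Change from Baseline in ECG is one of the named safety endpoints, and the SAP specifies no within-subject ECG change, unlike the two measures named beside it. The Hour 3 table, read with the SAP's own definition, has no placebo arm.

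The consequence is a safety endpoint not delivered as specified and a table that mixes persistent with new abnormalities. It does not touch the efficacy analysis. The sizes are illustrative: the 10-20% Baseline rate is assumed, the one-third variance reduction is a ceiling that applies only if intervals are recorded, and the safety analysis is descriptive. The conclusion itself rests on the text, not on these figures.

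**What to change.** Before the Day 42 blind break, amend SAP 9.12.4 as follows.

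1. Add by-arm shift tables from Baseline category (normal; abnormal, not clinically significant; abnormal, clinically significant) to Hour 3 and to Week 16. Count new or worsened abnormalities among subjects with both ECGs.
2. Run the Hour 3 table in all PK-subset subjects with an Hour 3 ECG, including placebo, and reconcile SAP 6.3 with SAP 5.1.
3. State one rule for the Baseline category from the triplicate that does not favour a worse Baseline. The last replicate keeps the comparison like for like; the majority category errs towards showing new findings. Do not use worst of three, and do not let the worst-value fallback in SAP 9.12 apply to the Baseline ECG.
4. If ECG intervals are in the database, summarise change from the mean of the Baseline replicates.

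If no change analysis is wanted, reword SAP 6.4 and record the departure in SAP 1.2.

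The cost is SAP wording and two descriptive tables from data already collected, plus an interval summary if item 4 applies. No new ECG is needed.

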9.12.5 Pregnancy Test

Pregnancy test details and results will be listed.

9.12.6 Physical Examinations

Physical examination data will be listed for the full assessment carried out at Screening and the abbreviated assessments post-Screening.

9.12.7 Safety Follow-Up After Day 42

The analysis of TEAEs collected during the extended safety follow-up after Day 42 will be similar to those described in Section 9.12.1.3. Should the number of TEAEs reported during the extended follow-up not warrant aggregate summaries, then the data will be reported as line listings only. Interpretation of these extended safety data will be compared and contrasted to the safety data collected through Day 42 including continuing TEAEs that resolved or continued during the extended safety follow-up. Physical exams and pregnancy test results will be listed along with any laboratory. Vital signs and ECG summary tables will be reissued at the Week 16 analysis to include assessments completed at Week 16.

9.12.8 Subgroup Analyses

Safety summaries for All TEAEs and TEAEs by SOC and PT will also be provided for the following subgroups if the sample size within subgroups is sufficient:

- Age (18 to 64 and ≥ 65)
- Gender
- Race
- Ethnicity
- Region

11 TIME AND EVENTS SCHEDULE OF STUDY PROCEDURES

Assessment	Screening (Day -7 to Day -1)	Day 0 In-clinic				Day 7 By phone	Day 14 In-clinic	Day 28 In-clinic	Day 42 In-clinic	Week 12 By phone	Week 16 In-clinic
		Pre- dose	Hour 0	Hour 3	Hour 10						
Visit window	N/A	N/A	N/A	± 30 minutes	± 2 hours	± 1 day	± 2 days	-2/+4 days	± 2 days	± 7 days	± 7 days
Informed consent	X										
Inclusion/exclusion criteria	X	X									
Scabies diagnosis ¹	X										
Medical history	X										
Physical examination ²	X						X	X	X		X
Vital signs ³	X	X					X	X	X		X
12-lead ECG		X ⁴									X
Height	X										
Body weight	X										
Pregnancy testing ⁵	X	(X)									X
Pharmacokinetic blood sample collection ⁶				X	X			X	X		
Hematology and serum chemistry	X						X	X			X ⁷
Scabies assessments		X						X			

¹ Scabies will be diagnosed upon clinical findings typical of active scabies infestation (burrows, typical inflammatory/noninflammatory lesions) and either microscopic or dermatoscopic confirmation of scabies mite, ova or mite feces.

² A full physical examination will be performed at Screening. At all subsequent time points, a symptom-based physical examination (informed by concurrent conditions, signs and symptoms, and adverse events reported) will be performed.

³ Vital signs (supine blood pressure, heart rate, respiratory rate, and body temperature) will be measured after the subject has rested for approximately 5 minutes.

⁴ Standard 12-lead safety electrocardiograms will be performed after the subject has been supine for approximately 10 minutes at Baseline before randomization. An additional 12-lead ECG will be conducted 3 hours post dose in the subjects selected for pharmacokinetic blood sampling. ECGs will be performed before blood collection.

⁵ Serum pregnancy test at Screening and urine pregnancy tests during study. A pregnancy test on Day 0 will only be conducted if Screening was conducted more than 24 hours prior to Day 0.

⁶ PK sample collection will occur in a subset of approximately 20 subjects per arm selected at randomization. On Day 0, PK samples will be collected at 3 hours ± 30 minutes and 10 hours ± 2 hours.

⁷ If clinically relevant abnormalities were identified in safety hematology or serum chemistry at Day 28.

CONFIDENTIAL

Page 37 of 45

Assessment	Screening (Day -7 to Day -1)	Day 0 In-clinic				Day 7 By phone	Day 14 In-clinic	Day 28 In-clinic	Day 42 In-clinic	Week 12 By phone	Week 16 In-clinic
		Pre- dose	Hour 0	Hour 3	Hour 10						
Visit window	N/A	N/A	N/A	± 30 minutes	± 2 hours	± 1 day	± 2 days	-2/+4 days	± 2 days	± 7 days	± 7 days
Randomization ⁸		X									
Investigational product administration ⁹			X								
Adverse events ¹⁰	X	X	X	X	X	X	X	X	X	X	X
Prior and concomitant medications	X	X	X	X	X	X	X	X	X	X	X

⁸ Randomization will occur after subject eligibility has been confirmed on Day 0.

⁹ Investigational product administration will occur after an overnight fast of at least 8 hours. Investigational product will be administered with at least 240 milliliters of water. No food will be allowed for 60 minutes after dosing; however, clear liquids can be taken ad libitum.

¹⁰ Adverse events will be reported from informed consent onwards.

12 APPENDICES

Appendix 1: Fixed Imputation for Non-Informative Missing Day 28 Complete Cure Endpoints

For subjects missing a Day 28 Complete Cure endpoint because of non-informative reasons, their endpoint will be imputed as a non-responder or responder using a logistic regression. The process will follow the following steps:

1. Run a logistic regression model using FAS subjects with non-missing Day 28 responses. This will include those subjects whose Day 28 response was imputed because of informative missing data.
2. Using the coefficients from the logistic regression, calculate the probability of achieving a Day 28 Complete Cure for those subjects with missing outcomes due to non-informative missing.
3. If the predicted probability for the subjects with non-informative missing is > 0.50 then impute a responder/cured status for their Day 28 Complete Cure endpoint.
4. If the predicted probability for the subjects with non-informative missing is ≤ 0.50 then impute a non-responder/not cured status for their Day 28 Complete Cure endpoint.

The logistic model will include demographic and baseline covariates and is pre-specified to include randomized treatment group as listed below. Should the logistic regression fail to converge, or produce unreliable coefficients/SEs because of multicollinearity or other reasons, a backward stepwise selection of covariates for removal will be conducted until the logistic model converges. The backward stepwise model will begin by using a significance level for removal of 0.10. If the model still does not converge the significance level for removal will be set to 0.05. Randomized treatment group will be a "locked" covariate and not eligible for removal. If the logistic regression model still fails after attempts at backward elimination, the observed proportions of Complete Cure responders in each randomized treatment group will be calculated across all regions and including any "informative" imputations, but excluding the non-informative missing data subjects. For the non-informative missing data subjects, if the observed proportion for their randomized treatment group is > 0.50 they will be imputed as achieving Complete Cure at Day 28. If the observed proportion for their randomized treatment group is ≤ 0.50 they will be imputed as not achieving Complete Cure at Day 28.

Logistic Regression Model Covariates:

- Region
- Randomized Treatment Group
- Age
- Gender
- BMI
- Race (collapse or eliminate if too sparse)
- Previous history of scabies
- Number of lesions
- Evidence of burrows
- Evidence of pruritus

- Number of regions affected

The steps in the backwards stepwise model along with the final model covariates, coefficients, SEs and p-values will be provided.

Appendix 2: Non-Informative Missing - Multiple Imputation for Complete Cure

As described in Section 9.11.2, if the percent of FAS participants whose Day 28 Complete Cure (ComC) outcome is missing due to non-informative reasons exceeds 5%, the ComC outcome for these subjects will be imputed using multiple imputation (MI) for the primary efficacy analysis. The implementation of the MI will proceed according to the steps outlined below. The MI process described here also includes the individual treatment group point estimates of the ComC and the three exploratory pairwise comparisons comparing each moxidectin dose group to the other moxidectin dose groups.

All of the MI datasets, as well as the bootstrapped sampled datasets, will be available. Complete documentation of the seed(s) and program code for the imputation, bootstrap and final derivation of the MI estimators will be such that the imputed and bootstrapped datasets may be replicated. Should the imputation model fail to converge, produce unreliable SEs, or irrational imputations, the imputation for non-informative missing subjects will default to the methods outlined in Appendix 1.

Step 1: Derivation of the MI FAS Dataset

Define the MI FAS dataset as FAS subjects with an observed Day 28 ComC or a non-informative missing Day 28 ComC. Leave the missing Day 28 ComC for non-informative missing subjects as missing. For the MI FAS dataset, include subjects exposed to scabicides prior to Day 28 whether their Day 28 endpoint is observed or not and set their ComC to Not Cured. Exclude any subject missing a Day 28 ComC that is considered “informative” missing.

Step 2: Definition of the Imputation Model

Define the imputation model imputing the Day 28 ComC outcome, to be a logistic regression with the following covariates:

- Region
- Age
- Gender
- BMI
- Race (collapse or eliminate if too sparse)
- Previous history of scabies
- Number of lesions
- Evidence of burrows
- Evidence of pruritus
- Number of regions affected

If the model does not converge or fails, stepwise backward elimination will be implemented, similar to that outlined in [Appendix 1](#).

Step 3: Generate M=50 Multiple Imputed Datasets

- Using the MI FAS data set in Step 1 and the imputation model in Step 2 above, generate 50 multiple imputed datasets stratified by randomized treatment group i.e. multiple imputed independently for each randomized treatment group (200 datasets total). Should

CONFIDENTIAL

the imputation model fail to converge or produce unreliable SEs, or irrational imputations for any of the randomized treatment groups, the imputation for non-informative missing subjects will default to the methods outlined in [Appendix 1](#) and no further attempts at MI will be made. If the imputation model is successful in generating the MI datasets continue with the remaining MI Steps.

- For each of the 50 imputation runs, append the 4 randomized group datasets together forming a single MI dataset that contains the data for all four treatment groups resulting in 50 datasets.
- Subjects with missing ComC due to “informative” reasons, and initially excluded from the MI FAS dataset, will now be added to each of the 50 MI datasets with their missing ComC outcome set to Not Cured for each of the 50 datasets.
- Refer to these M=50 datasets as the Final MI datasets.

Step 4: Derive the MI Estimator for the Average Predicted Probability for each Treatment Group and the Risk Difference for Each Pairwise Comparison (Substantive Model)

For each of the Final 50 MI datasets from Step 3 above, each of which now contains all FAS subjects, calculate the Average Predicted Probabilities for each randomized treatment group and the Risk Difference for all six pairwise comparisons using the methods outlined in [Section 9.11.1](#). The six pairwise comparisons include the three primary analysis pairwise comparisons of each moxidectin dose group to placebo and the three pairwise comparisons of each moxidectin dose group to the other moxidectin dose groups.

Step 5: Derive the Bootstrapped SEs for the MI Estimator of the Group Average Predicted Probabilities and the Pairwise Risk Differences

For each of the Final 50 MI datasets using the methods outlined in step 3, generate B=1000 bootstrapped samples (with replacement) to calculate the SEs for the Average Predicted Probabilities and the Risk Differences calculated in Step 4.

Step 6: Use Rubin’s Rule to Derive the MI Estimators and SEs

Using Rubin’s Rule ([Carpenter, J.R. and Kenward, M.G. 2013](#)) generate the MI estimators and their variances/SEs for the Average Predicted Probabilities for each randomized treatment group and the Risk Difference for all six pairwise comparisons across the 50 MI datasets calculated in Step 5.

Step 7: Calculate p-values and 95% CI for the MI Estimators

- **Primary Efficacy Analysis: Pairwise Comparison of each Moxidectin Group to Placebo**

Using the MI estimators of the Risk Difference and their variances/SEs, calculate Wald tests and 95% CIs for each the three pairwise moxidectin comparisons against placebo using the Z value corresponding to Dunnett’s two-tailed adjusted alpha of 0.019.

- **Exploratory Efficacy Analysis: Pairwise Comparison of Each Moxidectin Group to Each Other**

Using the MI estimators of the Risk Difference and their variances/SEs,, calculate Wald tests and 95% CIs for each of the three pairwise comparisons comparing each

moxidectin group to the other moxidectin groups using the Z value corresponding to a two-tailed unadjusted alpha of 0.05.

- **Average Predicted Probabilities for each Randomized Treatment Group**

Using the MI estimators and the variances/SEs for the Average Predicted Probabilities for each randomized treatment groups, calculate the 95% CI for each treatment group using the Z value corresponding to a two-tailed unadjusted alpha of 0.05.

